### 3.8.5.2 Ophthalmologic

3.8.5.2.1 If ocular involvement, restage same schedule as with MRI

3.8.5.2.2 If no ocular involvement, examine for lymphoma if clinically indicated

### 3.8.5.3 FDG-PET

3.8.5.3.1 End of cycle 1

3.8.5.3.2 At the time of complete response (or CRu) by MRI criteria

- Due to scheduling, may be done at following cycle

3.8.5.3.3 End of cycle 6 if best response less than CRu, otherwise, end of cycle 8

3.8.5.3.4 At month 12 at time of MRI

3.8.5.3.5 At the time of suspected disease recurrence/progression by MRI criteria following complete response and previous negative FDG-PET

### 3.8.5.4 Cerebrospinal Fluid

3.8.5.4.1 At the time of complete response (or CRu) by MRI criteria

- Due to scheduling, may be done at following cycle

3.8.5.4.2 At the time of suspected disease recurrence/progression by MRI criteria

- Ig PCR and EBV PCR (Molecular Pathology, [name], 2N116-A)
- Flow cytometry ([name], Room B1 B58)
- Cytopathology
- Quantitative EBV PCR (CC Microbiology)
- Cell count with differential, glucose, protein

3.8.5.4.3 At end of treatment and at 6 months post treatment:

- Ig PCR and EBV PCR ([name])
- Quantitative EBV PCR (CC Microbiology)
- Cytopathology
- Flow cytometry ([name], Room B1 B58)
- Cell count with differential, glucose, protein

### 3.8.6 Neuropsychometric testing

3.8.6.1 Folstein Mini-Mental Status Examination will be done for comparative purposes prior to therapy, after cycle 1, and again at completion of treatment course.

3.8.6.2 Baseline formal neuropsychologic assessment will be administered 1-2 months after completion of chemotherapy treatment course.

3.8.6.3 Follow-up assessments will be administered at 6, 12, 18, 24, and 36 months ( $\pm$  3 months) after completion of therapy. Comprehensive assessment will be performed at the post-therapy baseline and annually thereafter whereas monitoring assessments will be administered at the half-year evaluations (see [Appendix 5](#) for the comprehensive and monitoring neuropsychologic test

batteries).

### 3.8.7 Adherence Assessment

3.8.7.1 At 1-2 months after completion of therapy, patients will complete measures assessing barriers to adherence, knowledge of HIV, and perceived social support (see [Appendix 6](#) and [Appendix 7](#)).

3.8.7.2 A follow-up knowledge and social support assessment will be administered at 6 months. Follow-up adherence assessments (via self-report) will be conducted every 3 months, beginning 3 months post-treatment through month 24. Results from these data will guide interventions aimed at identifying patterns of non-adherence and specific barriers identified by the patient as being problematic.

### 3.8.8 Optional Blood Draws

Up to 50 cc of blood may optionally be drawn for immunological testing, establishment of cell lines, evaluation of hematologic parameters, or other studies that become clinically important during conduct of the trial. However, this should not be drawn if it brings the total amount of blood drawn to more than 450 mL during a 6-week period. Blood and tissue specimens collected in the course of this research project may be banked and used in the future to investigate new scientific questions related to this study. However, this research may only be done if the risks of the new questions were covered in the consent document or are of minimal risk. If new and significant risks are associated with the research (e.g. analysis of germ line genetic mutations) the principal investigator must obtain IRB approval. Handling of optional biospecimens is outlined in Section [7.5](#).

## 3.9 CONCURRENT THERAPIES

### 3.9.1 Anti-retroviral therapy

See section [3.6.2](#)

### 3.9.2 Contraception

All females of childbearing potential will be given contraception or provided with barrier contraceptive devices.

### 3.9.3 Pneumocystis jiroveci prophylaxis (PJP/PCP)

All patients will receive PCP prophylaxis throughout the treatment period and until the CD4+ cells are sustained over 200 cells/mm^3 for a 3-month or longer period of time.

If cotrimoxazole (trimethoprim+sulfamethoxazole; Bactrim®) is used, it should be withheld during methotrexate treatment until completion of leucovorin rescue.

Alternatives include:

- Dapsone 50 – 100 mg PO daily or 100 mg PO 2x/week
- Aerosolized pentamidine 300 mg by inhalation, monthly
- Atovaquone 750 mg PO BID

### 3.9.4 MAC prophylaxis

Essentially all patients on study will require prophylaxis since AR-PCNSL occurs in those with CD4+ cells <50/mm^3.

Azithromycin 1200 mg orally once weekly is recommended, but other agents are

acceptable.

### 3.9.5 Antibacterial Prophylaxis

For patients with anticipated severe neutropenia (ANC <500 cells/mm^3) related to cyclic chemotherapy, consider levofloxacin 500 mg PO daily for up to seven consecutive days, timed to coincide with periods of severe neutropenia that cannot be managed with filgrastim.

### 3.9.6 Hepatitis B antigenemia

For patients with serologic evidence of chronic persistent/active HBV infection, lamivudine 150 mg PO daily, tenofovir 300 mg PO daily, or other agents with demonstrated anti-HBV activity should be given continually throughout treatment cycles until a medically-responsible investigator advises discontinuation. Since chemotherapy in general and rituximab in particular are associated with HBV reactivation, this should also be considered in patients with anti-HB core-alone positivity.

### 3.9.7 Contraindicated therapies

Trimethoprim/sulfamethoxazole should not be given within 48 hours prior to methotrexate administration and until methotrexate concentration is <0.05 mcg/L.

Methotrexate should not be given concurrently with any of the following medications without the approval of a medically responsible study investigator:

1. Asparaginase
2. Aspirin
3. Acidic drugs
4. Amoxicillin
5. Cephalosporins
6. Chloramphenicol
7. Cholestyramine
8. Cotrimoxazole
9. Cyclosporine
10. Diclofenac
11. Ibuprofen
12. Indomethacin
13. Ketoprofen
14. Mercaptopurine
15. Mezlocillin
16. Naproxen
17. Non-steroidal anti-inflammatory drugs
18. Omeprazole
19. Penicillins
20. Piperacillin ( $\pm$ tazobactam)
21. Probenecid
22. Proton pump inhibitors (e.g., dexlansoprazole, esomeprazole, lansoprazole, omeprazole, pantoprazole, rabeprazole)
23. Pyrimethamine
24. Salicylates
25. Sulfonamides
26. Sulindac
27. Tetracyclines
28. Tolmetin
29. Trimethoprim
30. Trimethoprim/sulfamethoxazole
31. Vaccines, Live (viral and bacterial)

Generally, these agents should be withheld 48 hours prior to the initiation of methotrexate and until methotrexate concentration is  $<0.05$  mcg/L.

### **3.10 RADIATION THERAPY GUIDELINES**

- 3.10.1 Radiation therapy to the brain will be deferred in all patients unless there is progression of disease with high-dose methotrexate- rituximab, or radiation-sparing best therapy, stable disease or partial response as best response to high-dose methotrexate- rituximab or radiation-sparing best therapy, or recurrence following apparent complete response with high-dose methotrexate- rituximab or

radiation-sparing best therapy, and further chemotherapy approaches by themselves are not assessed by the treatment team to be clinically appropriate. Patients requiring radiotherapy (or any other additional therapy for AR-PCNSL) will be considered treatment failures for this study. Patients requiring such therapy will be returned to the care of the referring physicians when possible. If possible, continuation of neuropsychometric testing outlined in the study will continue, to describe the cognitive outcome.

3.10.2 Radiation following high-dose methotrexate may confer additional risk of neurotoxicity. For this reason, when feasible, salvage chemotherapy strategies will be considered as appropriate.

3.10.3 Progressive disease

3.10.3.1 Alternative chemotherapy or WBRT to achieve best tumor control.

3.10.4 Partial Response

3.10.4.1 Limited volume RT (if possible) to achieve best tumor control and limit CNS exposure and late term radiation-related neurotoxicity.

3.10.5 Early Recurrence

3.10.5.1 Minimal disease will be treated with limited volume RT if possible, to achieve best tumor control and limit CNS exposure and late term radiation-related neurotoxicity. WBRT will be utilized if indicated.

3.10.6 Diffuse recurrence may be treated with WBRT if indicated to achieve best tumor control

## **3.11 CRITERIA FOR REMOVAL FROM PROTOCOL THERAPY AND OFF STUDY CRITERIA**

Prior to removal from study, effort must be made to have all subjects complete a safety visit approximately 30 days following the last dose of study therapy.

3.11.1 Criteria for removal from protocol therapy

- Completion of therapy
- Dose delays in excess of 15 days
- Withdrawal of consent
- Inability to tolerate HAART or other oncologic therapies

See Section 3.5 for additional criteria for discontinuing rituximab and high-dose methotrexate with leucovorin rescue.

3.11.2 Off Study Criteria

- Refusal to adhere with HAART
- Refusal of oncologic therapy
- Patient or patient advocate (if patient not competent) voluntary withdrawal
- Progression of disease and either refusing or not eligible to receive second-line chemotherapy AND/OR radiotherapy
- Progressive, irreversible neurocognitive deficits, not attributed to AIDS-PCNSL or treatable infection, occurring greater than 90 days after the completion of

radiation therapy that would be scored as grade 3 or higher by the RTOG/EORTC Late Radiation Morbidity Scoring Scheme

- Completion of 5 years follow-up with no recurrent AR-PCNSL

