#### 1.1.2 Secondary

1.1.2.1 To describe the acute toxicities associated with administering a regimen of high-dose methotrexate with leucovorin and rituximab with HAART in patients with AR-PCNSL

1.1.2.2 To estimate the complete response rate, progression-free, disease-free, and overall survivals to high-dose methotrexate with leucovorin and rituximab given with HAART in patients with AR-PCNSL

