1.1.2.3 To describe HIV disease, EBV infection, and lymphoma tumor biology

1.1.2.4 To assess the neurotoxicity associated with this regimen by monitoring neuropsychologic function over time through longitudinal psychometric testing

1.1.2.5 To assess overall survival, progression-free survival, and long-term neurocognitive outcomes in patients with AR-PCNSL in who high-dose methotrexate is contraindicated and are therefore treated with radiation-sparing therapy consisting of dose-modified, dose-dense rituximab combined with HAART but no high-dose methotrexate.

1.1.2.6 To assess overall survival and long-term neurocognitive outcomes in patients with AR-PCNSL who receive “Radiation Sparing Best Available Care”, consisting of HAART and any additional first or second line radiation-sparing approaches

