### **3.7 SECOND-LINE THERAPY**

Second-line chemotherapy AND/OR radiotherapy assessment and treatment may be included as part of the protocol when necessary for best patient care; in such a case, patient can remain on-study if they are evaluable for disease specific and overall survival endpoints. Importantly, such patients will be assessed for long-term neurocognitive outcomes using protocol defined neuropsychometric testing. This will be to assess in an observational manner late term neurotoxicity should the patient survive long enough to manifest this complication. Patients receiving radiation therapy will be evaluated separately in regards to neuropsychometric testing. As noted in section 3.6 and 5.3.6, patients requiring radiotherapy will be considered treatment failures for statistical purposes of the protocol. If patient is unable or unwilling to participate in neuropsychometric testing, patient will remain on study until completion of second-line therapy at NCI or until referral to another facility, whichever is first.

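### Patients who leave the study at untreated progression, refusal or referral have no required vital-status follow-up, so exploratory overall survival is biased upward if progression exits are censored at exit

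*Combined protocol and SAP*

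**What the plan says.** **Objective.** Section 1.1.2.2 sets out "To estimate the complete response rate, progression-free, disease-free, and overall survivals" for the methotrexate regimen. Section 1.1.2.5 sets out "To assess overall survival, progression-free survival, and long-term neurocognitive outcomes in patients with AR-PCNSL" for patients in whom methotrexate is contraindicated, and 1.1.2.6 adds overall survival under other radiation-sparing care. Section 6.1.3 makes all secondary endpoints exploratory.

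**Exits.** The off-study list in 3.11.2 includes "Progression of disease and either refusing or not eligible to receive second-line chemotherapy AND/OR radiotherapy", "Refusal to adhere with HAART" and "Refusal of oncologic therapy". Under 3.7, a patient on second-line treatment may stay: "patient can remain on-study if they are evaluable for disease specific and overall survival endpoints". If that patient cannot or will not do neuropsychometric testing, "patient will remain on study until completion of second-line therapy at NCI or until referral to another facility, whichever is first". Section 3.10.1 says of patients needing radiotherapy or other additional lymphoma therapy: "Patients requiring such therapy will be returned to the care of the referring physicians when possible". Their neuropsychometric testing continues if possible.

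**After exit.** Section 3.11 asks for an attempt at a safety visit about 30 days after the last dose, before removal. Section 3.11.3 asks for a notice and a status form to the registration office. The three-year schedule in 3.12.1 is worded as on-study follow-up.

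**Censoring.** Section 6 gives no time origin, estimator or censoring rule for overall survival. The only censoring text is in 1.2.5. It says that patients who fail to keep HIV viral load low, and as a result have HIV complications that can affect neurocognitive function, will be censored when this becomes evident and can be replaced. It names no endpoint.

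**The concern.** A patient who progresses and receives no further treatment probably has a worse outlook than one who stays in follow-up. If follow-up ends at that point and the patient is censored there, the censoring is related to prognosis. Kaplan-Meier then gives the departed patient the survival of those who remain, and the estimate is too high.

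No decision rule uses overall survival. However, 6.1.3 says that the results will be weighed against other studies when further development is considered. A survival figure that misses deaths after progression is not comparable with one that includes them. Dates of death that are not collected may be hard to recover later.

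**Working it through.** **1. The plan's own figure.** The stated 88% power belongs to the primary endpoint and reproduces. For n=15 and a null rate of 30%, success at 8 or more has exact one-sided alpha 0.0500 (7 or more gives 0.131, above 0.10). Power at 65% is 0.887. Nothing below changes this.

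**2. Does any text capture deaths after exit?**

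| Section | What it covers | Where it stops |
|---|---|---|
| 3.12.1 | scheduled evaluations | worded as on study |
| 5.1 | adverse events | 30 days after removal from treatment or off study, whichever is first |
| 8 | serious adverse events | while on study |
| 8.2.1 | deaths other than from progressive disease | 30 days after last dose |
| 8.2.2 | all Grade 5 events | same 30-day window |

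Deaths inside these windows are captured. A death after both the 30-day window and the off-study date is not required to be.

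**3. Worked case that needs no exit rate.** Take 15 patients, with deaths at 3, 6, 9, 12, 15, 18 and 21 months and 8 alive at 36 months. With full follow-up, KM(24) = 8/15 = 53.3%. Now censor a death 2.5 months before it occurs.
- One lost death: the earliest gives 8/14 = 57.1% and the latest gives 9/15 = 60.0%. The mean over all seven choices is 58.4%.
- Two lost deaths: the earliest pair gives 8/13 = 61.5% and the latest pair gives 10/15 = 66.7%. The mean over all pairs is 63.8%.

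Each lost death therefore adds about 5 points.

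**4. Average bias under assumed exit shares.** The documents give no exit rate, so every input here is an assumption. Death times are exponential with two-year survival 50%, n=15, and administrative censoring is at 36 months. A share f of patients is marked to leave before death, by an exponential gap with median g months. An exit drawn before enrolment is impossible, so it is not counted and that death is observed. The fraction so removed is g/(g+24): 2.5/26.5 = 9%, 6/30 = 20% and 12/36 = 33%. The effective share is lower than the nominal one by that fraction. Bias is the mean KM(24) minus the mean under full follow-up, in points:

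| Median gap | f = 5% | f = 10% | f = 20% |
|---|---|---|---|
| 2.5 months | +1.3 | +2.8 | +5.7 |
| 6 months | +1.0 | +1.9 | +3.9 |
| 12 months | +0.5 | +1.1 | +2.3 |

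A program that leaves the impossible exits in overstates the 20% column as +6.8, +6.1 and +5.3.

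For scale, the sampling SD is √(0.5×0.5/15) = 12.9 points. At f = 20% and g = 2.5, the expected number of exits within 24 months is 15 × 0.20 × (24/26.5) × 0.5 = 1.4 patients. Only the progression exit is modelled; referral and refusal exits are not.

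**5. Direction under a different model.** This illness-death model has exit at progression itself. It uses 24-month event-free rates of 65% or 30% (borrowed from the design), 70% of first events being progressions, and post-progression medians of 3, 6 or 12 months. The bias was upward in all 18 settings. With a quarter of progressors leaving it was about +2 to +6 points. These inputs are also assumed.

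**The case against.** **The exits are narrow.** Progression alone does not end participation; second-line treatment must also be refused or not possible. Sections 3.6.3.1 and 3.6.3.2 let patients on second-line chemotherapy or radiotherapy be followed while they stay on HAART and are evaluable for neurocognitive outcome, and 3.7 allows retention for survival. The referral exit applies only to patients not doing testing. Section 3.10.1 does not say that patients returned to referring physicians go off study. This stands, and it is why large biases cannot be claimed. The retention wording is permissive, however, and does not reach a progressor who receives no second-line treatment.

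**Vital status may be known anyway.** The documents show some contact routes: co-enrolment in 01-C-0038 (3.8.1.4, 3.8.3, 7.5.10), concurrent NIAID protocols (1.2.6) and continued testing under 3.10.1. These make complete loss less likely, but none requires survival capture after exit. Consent pages, which might cover later contact, could not be checked.

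**No rule says to censor at exit.** This is correct. A reader might infer that the plan censors overall survival at progression. It does not say so: 1.2.5 concerns HIV failure and names no endpoint. The bias is a risk left open by silence.

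**The endpoint is exploratory, and 1 to 3 points is small against an SD of 13.** This is true at shares of 5-10%. Exploratory status excuses imprecision, but it is a weak reason to leave a bias of known direction in place when it is so cheap to avoid.

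**Conclusion.** The concern holds in a limited form. The plan allows exits related to prognosis, requires no vital status afterwards, and sets no censoring rule specific to overall survival. If progression exits are censored at exit, overall survival is overstated. The direction rests on the plausible assumption that those who leave at untreated progression die sooner than those who stay.

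The size is unknown. It is about 5 points per lost death in a 15-patient cohort, and on average about 0.5 to 6 points over the assumed grid. A reader might infer a much larger bias by supposing that a third or half of deaths follow such an exit. No section supports such shares.

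A reader might also infer that the primary result is compromised. For progression exits it is not: 5.3.6 already counts progression as failure, so N=15 and the stated power stand. The opposite reading, that the primary endpoint is wholly untouched, goes too far. Section 5.3.6 does not clearly class a patient who leaves in remission for refusing HAART, and that patient's two-year status may be unknown.

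Severity is minor to moderate: this is a cheap improvement to an exploratory estimate.

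**What to change.** In 3.7 and 3.11.2, separate off-study status from survival follow-up. For all enrolled patients, collect date of death or date last known alive through the planned 3 years, by telephone or referring-physician contact, unless consent to contact is withdrawn.

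In section 6, state the overall survival time origin and censoring rule, reconcile that rule with the censoring sentence in 1.2.5, and report the number censored at exit by reason. A sensitivity analysis counting progression exits as deaths at the off-study date is optional; it leans low and would serve as a conservative companion figure.

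No treatment or off-study criterion changes. The cost is amendment wording, a few contacts for at most 28 patients (the accrual ceiling), consent wording if later contact is not already permitted, and possibly a less favourable survival figure.

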### 3.11.3 Off Protocol Therapy and Off-Study Procedure

Authorized staff must notify Central Registration Office (CRO) when a subject is taken off protocol therapy and when a subject is taken off-study. A Participant Status Update Form from the web site (<http://home.ccr.cancer.gov/intra/eligibility/welcome.htm>) main page must be completed and sent via encrypted email to: NCI Central Registration Office [[contact]](mailto:[contact]).

## 3.12 POST-STUDY EVALUATION

- 3.12.1 Patients will be followed on study for 3 years on protocol (see [Appendix 3](#)). After the end of the three-year period, patients may be followed for clinical assessment on an annual basis for up to a total of 5 years. Specific additional assessments will be determined according to clinical findings at that time, and in concert with referring physicians.
- 3.12.2 Patients followed in the “Radiation-sparing Best Available Care” cohort will be followed using the same schedule as those receiving protocol defined therapy.

## 4 SUPPORTIVE CARE

### 4.1 PNEUMOCYSTIS JIROVECI PNEUMONIA

Patients who develop PCP will receive standard of care including trimethoprim-sulfamethoxazole, steroids when appropriate and alternative standard agents such as IV pentamidine, atovaquone, or trimetrexate in combination with leucovorin when trimethoprim-sulfamethoxazole cannot be used. Trimethoprim-sulfamethoxazole must be held during administration of high dose –methotrexate and leucovorin rescue, as outlined in Section [Contraindicated therapies3.9.7](#).

### 4.2 CYTOMEGALOVIRUS (CMV)

Periodic ophthalmologic evaluations will be conducted on all patients, as this subset of AIDS patients are at particular risk of CMV retinitis. Baseline examination will be conducted as soon as possible at entry, and then approximately every 1-3 months until the CD4+ cells are over 75 cells/mm^3. Ganciclovir ocular implants will in general be the initial treatment choice. Intravenous ganciclovir or oral valganciclovir can be considered, but due to its hematological toxicity, it should not be used without consulting the PI or LAI. Both cidofovir and foscarnet are effective in CMV, but are nephrotoxic, and will not be used during high-dose methotrexate. Urinalysis for proteinuria and creatinine clearance estimates or measurements made if these agents are to be used. All cases of CMV infection must be discussed with the PI or LAI.

### 4.3 FUNGAL INFECTIONS

- 4.3.1 Oral Candidiasis – if asymptomatic, recommend clotrimazole troches. If symptomatic, recommend oral fluconazole.
- 4.3.2 Esophageal Candidiasis – recommend oral fluconazole, but if no response,

consider itraconazole, amphotericin B.

4.3.3 Aspergillosis, scedosporiosis and other invasive fungal infections infection may present as meningitis, pneumonia, or fungemia. Treatment decisions will be made in concert with infectious disease consultants, and may include the use of agents such as voriconazole, liposomal amphotericin B, or other novel agents as the clinical presentation requires.

